### 8.2.2 Adverse events

Treatment-emergent AEs (TEAE) are defined as those events which start on or after the date of first LCM administration and within 30 days following the date of last LCM administration, or whose severity worsens within this time frame.

Other significant AEs are defined in Appendix 13.1 (Table 13-1).

An overall summary of AEs will provide the numbers and percentages of subjects with at least 1 TEAE, serious TEAE, other significant TEAE, TEAE that led to discontinuation, drug-related TEAE, drug-related serious TEAE, severe TEAE, AE leading to death, and TEAE leading to death. The AE overall summary will be repeated by syndrome subgroups (as described in Section 4.8).

The following summaries of AEs will be provided by primary SOC and PT:

- TEAEs
- TEAEs during the Titration Period
- TEAEs during the Maintenance Period
- TEAEs by syndrome subgroups (as described in Section 4.8)
- TEAEs including subject numbers

- Serious TEAEs
- Serious TEAEs including subject numbers
- TEAEs leading to discontinuation
- TEAEs leading to discontinuation including subject numbers
- TEAEs by maximum intensity
- Nonserious TEAEs
- Nonserious TEAEs occurring in > 5% of subjects
- Other significant TEAEs

The following summaries by primary SOC and PT will be presented overall only (ie, not by age group).

- TEAEs by relationship to LCM
- Serious TEAEs by relationship to LCM
- Nonserious TEAEs by relationship to LCM
- Fatal TEAEs by relationship to LCM
- Nonserious TEAEs occurring in at least 5% of subjects by relationship

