5.1.1 Study duration per subject

The duration of treatment for an individual subject may be up to approximately 18 weeks excluding the Taper Period.

The study will consist of a 6-week prospective Baseline Period, followed by a 6-week Titration Period and a 12-week Maintenance Period. Subjects may be eligible to enter an additional open-label study (SP848) after completion of the Maintenance Period. Subjects who do not complete the full 12 weeks of the Maintenance Period may still be eligible to enter the SP848 open-label study after consultation with the medical monitor. Subjects who do not continue in the open-label study will enter a 2- to 4-week Taper Period followed by a Safety Follow-Up Visit 2 weeks (±2 days) after the final dose of LCM and a Safety Follow-Up Telephone Contact 30 days (-1/+3 days) after the final dose of LCM. The total study duration for a subject will be up to a maximum of 32 weeks.

The start of the study is defined as the first visit of the first subject entering the study. The end of the study is defined as the date of the last visit of the last subject in the study.

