^d At the end of Visit 9 or at ET, all subjects who complete the Maintenance Period and whose daily dose was at least 4mg/kg/day for subjects weighing < 50 kg, and 200mg/day (tablets/oral solution) for subjects weighing ≥ 50 kg will be offered the opportunity to enroll in an additional open-label extension study, SP848. Visit 9 or the ET Visit of SP0966 will also serve as Visit 1 for SP848. Subjects who do not complete the full 12 weeks of the Maintenance Period may still be eligible to enter the SP848 open-label study after consultation with the medical monitor. Subjects who do not continue in the open-label extension study will complete the End of Study procedures that include a 2- to 4-week LCM taper followed by a 30-day Safety Follow-Up Period. Taper of LCM may not be

Table 5-1: Schedule of study assessments (Baseline Period, Titration Period, Maintenance Period, Taper Period, End of Study Period and Unscheduled Visit)

Assessments	Baseline Period (6 weeks)		Treatment (18 weeks)												End of Study Period		Unscheduled Visit ^a			
	Titration Period (6 weeks)						Maintenance Period (12 weeks)						Taper Period (2-4 weeks) ^b					Safety Follow-Up (30 days)		
Visit	V1	TC 1	V2	TC 2	V3	TC 3	V4 ^c	V5 ^c	End of Titration V6	TC 4	V7	TC 5	V8	TC 6	V9/ ET ^d	TC of Taper Visit ^f	Safety FU Visit ^g	Safety FU TC ^g	At any time	
Week in study	-6	-3	Day 1	1	2	3	4	5	6	8	10	12	14	16	18	19	20-22	22-24	24-26	

required for some subjects who discontinue study medication prematurely, depending on the treatment option selected by the investigator in consultation with the subject and/or parent/legal representative.

^e A telephone contact (T7) will be conducted at the end of the first week of the Taper Period.

^f Each subject will have only 1 Taper Visit. The Taper Visit will be scheduled at the end of the Taper Period (Week 20, Week 21, or Week 22, depending on dose level achieved; see Table 7-4 and Table 7-5). A time window of ± 2 days relative to Visit 2 (Titration Period) is applicable. The study week numbers provided are for subjects who complete the Maintenance Period and enter the Taper Period. The study week numbers provided do not apply to subjects who enter the Taper Period at other times.

^g The Safety Follow-Up Visit will occur 2 weeks (± 2 days) after the final dose of LCM. The Safety Follow-Up Telephone Contact will occur 30 days (-1/+3-days) after the final dose of LCM.

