8.4 End of Study Period

For subjects who enter the open-label study (SP848), the end of the study will be the date of the subject's last assessment in SP0966 (end of Maintenance Period or Early Termination Visit). Subjects who do not enroll in SP848 will enter a Taper Period followed by a Safety Follow-Up Period as described below, and the end of the study will be the date of the last Safety Follow-Up Telephone Contact.

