8.4.2 Safety Follow-up

Safety Follow-up is required only for subjects who do not enroll in the open-label study (SP848).

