11 ASSESSMENT OF SAFETY

11.1 Adverse events

11.1.1 Definition of AE

An AE is any untoward medical occurrence in a patient or clinical investigation subject administered a pharmaceutical product that does not necessarily have a causal relationship with this treatment. An AE can therefore be any unfavorable and unintended sign (including an abnormal laboratory finding), symptom, or disease temporally associated with the use of a medicinal (investigational) product, whether or not related to the medicinal (investigational) product.

In order to ensure complete safety data collection, all AEs occurring during the study (ie, after the signing of the ICF), including any pretreatment and posttreatment periods required by the protocol, must be reported in the eCRF even if no investigational product was taken but specific study procedures were conducted. This includes all AEs not present prior to the initial visit and all AEs that recurred or worsened after the initial visit.

Signs or symptoms of the condition/disease for which the investigational product is being studied should be recorded as AEs only if their nature changes considerably or their frequency or intensity increases in a clinically significant manner as compared to the clinical profile known to the investigator from the subject's history or the Baseline Period.

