#### **3.2 General study level definitions**

##### **3.2.1 Last dose of LCM**

Unless otherwise noted, all references to the last dose of LCM in this SAP refer to the last dose of LCM within the study (eg, including the Taper Period). The last dose of LCM during the Treatment Period will be defined as the last dose during the Titration and Maintenance Periods.

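### Syndrome-level TEAE percentages depend partly on the share of children entering SP848, because nonserious events after Visit 9/ET are observed only in those who do not enter it

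*SAP*

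**What the plan says.** - **Window.** SAP 8.2.2 (Adverse events) defines TEAEs as events that "start on or after the date of first LCM administration and within 30 days following the date of last LCM administration", or that worsen in that time. SAP 3.2.1 makes the last dose the last one taken in SP0966, taper included.
- **Children entering SP848.** Protocol 8.4 states that for them "the end of the study will be the date of the subject's last assessment in SP0966". A footnote to the schedule in Protocol 5.2 adds that "Visit 9 or the ET Visit of SP0966 will also serve as Visit 1 for SP848".
- **Follow-up.** Protocol 8.4.2 states: "Safety Follow-up is required only for subjects who do not enroll in the open-label study". Protocol 11.1.1 asks for AEs during the study, "including any pretreatment and posttreatment periods required by the protocol"; after Visit 9/ET no such period is required of a child entering SP848.
- **Children not entering SP848.** Protocol 8.4.1 and 8.4.2.2 give a taper of 2 to 4 weeks and a last telephone contact 30 days after the final dose. Taper may be omitted for some who stop early.
- **SAEs.** Protocol 11.2.2 requests SAEs from every subject up to 30 days after that subject's end of study.
- **Tables.** SAP 8.2.2 repeats the overall AE summary and the SOC/PT table by syndrome. SAP 3.1 makes summaries by age the default and uses numbers of subjects as denominators. SOC/PT tables for the Titration and the Maintenance Period are listed, but not by syndrome. No exposure-adjusted rate is planned.

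**The concern.** The TEAE definition is the same for every child, but the time over which a nonserious event could be recorded is not. It depends on whether the child entered SP848, and nothing in SAP 8.2.2 adjusts for that or displays it. Two syndromes with the same event risk could show different TEAE percentages only because different shares of their children continued.

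This matters because Protocol 5.4 gives the study the task of telling apart syndromes that benefit from those with no clear benefit or possible exacerbation. The added time covers dose reduction and time off drug, and events there enter the same syndrome percentage as events on a stable dose. The SAP handles other safety data differently: treatment-emergent laboratory values (8.5) and ECG abnormalities (8.6.2) are limited to the Treatment Period.

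**Working it through.** **Inputs from the documents**

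- Treatment: Protocol 5.1.1 says it "may be up to approximately 18 weeks excluding the Taper Period"; 6 weeks of titration plus 12 of maintenance = 18 weeks = 18 × 7 = 126 days.
- Taper: 14 to 28 days. Last contact: 30 days after the final dose.
- SP848 entry share and TEAE rates: not given, so assumed below.

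**The plan's own figure.** There is no sample size or power figure to reproduce. Protocol 5.1.1 states a maximum of 32 weeks per subject. Adding the periods: 6 + 6 + 12 + 4 weeks + 30 days (30/7 = 4.3 weeks) = 32.3 weeks. Only a child who does not enter SP848 and tapers for 4 weeks reaches it. A completer entering SP848 stops at 6 + 18 = 24 weeks.

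**Observed TEAE window for completers (nonserious events)**

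| Path | Days | Ratio to 126 |
|---|---|---|
| Enters SP848 | 126 | 1.00 |
| Not SP848, 2-week taper | 126 + 14 + 30 = 170 | 1.35 |
| Not SP848, 4-week taper | 126 + 28 + 30 = 184 | 1.46 |

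**Effect on a crude percentage.** Assume a constant hazard, and let p be the proportion with a TEAE by day 126. Over a window of w days the proportion is q = 1 − (1 − p)^(w/126). With SP848 entry share s, a syndrome made up of completers shows s·p + (1 − s)·q. Two such syndromes with the same p but entry shares of 90% and 40% (assumed) differ by (0.9 − 0.4)(q − p) = 0.5(q − p).

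| p | q at 170 to 184 days | Difference, 90% vs 40% entry |
|---|---|---|
| 10% | 13.3 to 14.3% | 1.6 to 2.1 points |
| 30% | 38.2 to 40.6% | 4.1 to 5.3 points |
| 50% | 60.7 to 63.7% | 5.4 to 6.8 points |

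**Sensitivity to the hazard.** If the hazard after treatment is m times the earlier one, q = 1 − (1 − p)^(1 + m(w − 126)/126). For p = 50%:

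- m = 0.25 gives q = 52.9 to 53.8%, so the 90% vs 40% difference is about 1.5 to 1.9 points.
- m = 2 gives q = 69.2 to 73.6%, so the difference is about 9.6 to 11.8 points.

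**Direction.** A child who stops early and does not enter SP848 is observed to the stopping day plus taper plus 30 days. That total is below 126 if the child stops before day 126 − 30 − 28 = 68 (4-week taper), 126 − 30 − 14 = 82 (2-week taper) or 126 − 30 = 96 (no taper). A low entry share caused by early dropout can therefore lower the percentage.

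**After the fix.** With onset limited to first dose through Visit 9/ET, every completer has 126 days and the ratio is 1.00.

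**The case against.** The strongest reply has five parts.

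1. **Period tables already exist.** TEAEs by SOC/PT for Titration and for Maintenance are planned, by age by default, and both leave out the post-treatment tail. This stands for age: a reader might infer that the age comparison has the same gap, but these tables largely cover it. They do not cover syndrome. They also cannot be summed into the percentage with at least one event, since a child may have events in both periods, and they lack the categories of the overall summary.
2. **The Treatment Period is not common to all.** SAP 3.2.3 ends it at ET for early withdrawals. This stands: the restriction equalises observation among completers only.
3. **Seizure worsening is measured elsewhere.** Seizure days per 28 days are normalised for time, split by period and repeated by syndrome (SAP 8.1.2). SAP 9.2 adds the proportions with marked increases. A reader might infer that worsening by syndrome would be misjudged. The documents do not support that, because these analyses exclude taper and follow-up.
4. **The window comes from the protocol, and taper is still exposure.** Protocol 13.3.2 sets the same definition, and children still take LCM during taper. Replacing the window would drop post-treatment deaths and SAEs from the syndrome tables. This stands, and it is why the remedy adds tables instead of replacing them.
5. **Chance dominates.** SAP 4.8 shows subgroups of as few as 4, where one child is 25 points. That is true, but it is no reason to leave in a systematic difference that is easily removed.

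**Conclusion.** The point holds for the syndrome-level TEAE summaries, and mainly for nonserious events, since Protocol 11.2.2 requests SAEs for 30 days after study end from every subject. Among completers the observed window differs by 44 to 58 days (ratio 1.35 to 1.46) according to SP848 entry and taper length, and no planned table removes this by syndrome.

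The window lengths follow from the documents; the effect on percentages does not. About 2 to 7 points rests on assumed entry shares of 90% and 40%, true rates of 10 to 50%, completers only and a constant hazard. A lower or higher hazard after treatment moves it either way.

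A reader might infer that a syndrome with few children entering SP848 must show more TEAEs. The documents do not support this: early withdrawals can have shorter windows, and intolerable AEs themselves require withdrawal (Protocol 6.3), so events may cause non-entry as well as follow from longer observation. This is an inexpensive improvement to a descriptive secondary display; it does not invalidate the safety analysis.

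**What to change.** Keep the protocol-defined 30-day TEAE tables as they are. In SAP 8.2.2:

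- Add the overall AE summary and the TEAE SOC/PT table by syndrome, restricted to onset in the Treatment Period of SAP 3.2.3, and base syndrome comparisons on these. Add the overall summary by age with the same restriction.
- Add one table of events with onset after the Treatment Period, with subjects not entering SP848 as the denominator. List separately any SAEs reported in that time for children who entered SP848.
- State that the restriction equalises observation among completers only, and that early withdrawals still have shorter windows.

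The cost is SAP wording and a few extra tables from data already collected. Study conduct does not change, and no post-treatment event disappears from the report.

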### 8.3 Exploratory safety variables

A frequency table will be presented for the number of subjects with a decrease of at least 30% and a decrease of at least 50% in generalized spike-wave discharges on 24-hour EEG at Visit 6 compared to Baseline by syndrome subgroups

### 8.4 Extent of exposure

The duration of LCM exposure for each study period will be calculated as follows:

Duration of LCM (days) = date of last dose of LCM during the respective period minus the date of first dose of LCM during the respective period plus 1.

For the calculation of the mean daily dose during the Maintenance Period, the total dose for each entry in the LCM administration form with at least 1 day within the Maintenance Period will be calculated as follows:

Total dose = (Morning dose + evening dose) x (administration stop date - administration start date + 1)

If the administration start date is before the start date of the Maintenance Period the start date of the Maintenance Period will be used instead. If the administration stop date is after the end date of the Maintenance Period the end date of the Maintenance Period will be used instead.

The mean daily dose during the Maintenance Period will be calculated as the sum of the total doses for each entry in the study medication administration form with at least 1 day within the Maintenance Period divided by the duration of LCM exposure during the Maintenance Period. Days during an analysis period with unknown dosing will be excluded from both the numerator and the denominator for the calculation of the mean daily dose.

The mean daily dose will be presented in mg/kg/day. For patients who received tablets, the mean daily dose will be normalized by the baseline weight.

The duration of LCM exposure will be summarized with descriptive statistics overall (ie, for the entire Treatment Period) as well as separately for each study period (Titration Period, Maintenance Period).

In addition, the duration of LCM exposure will be summarized in 14-day categories up to the scheduled duration of the period:

- Treatment Period:  $\leq 14$  days,  $>14-\leq 28$  days,  $>28-\leq 42$  days,  $>42-\leq 56$  days,  $>56-\leq 70$  days,  $>70-\leq 84$  days,  $>84-\leq 98$  days,  $>98-\leq 112$  days,  $>112-\leq 126$  days,  $>126-\leq 140$  days,  $>140-\leq 154$  days,  $>154-\leq 168$  days, and  $>168$  days.
- Titration Period:  $\leq 14$  days,  $>14-\leq 28$  days,  $>28-\leq 42$  days, and  $>42$  days.
- Maintenance Period:  $\leq 14$  days,  $>14-\leq 28$  days,  $>28-\leq 42$  days,  $>42-\leq 56$  days,  $>56-\leq 70$  days,  $>70-\leq 84$  days, and  $>84$  days.

The mean daily dose during the Maintenance Period will be summarized descriptively.

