5.4 Rationale for study design and selection of dose

Epilepsy is a condition for which an improved benefit/risk ratio for medicinal products remains a challenge; this is especially true for pediatric patients. Based on the demonstrated efficacy and safety of LCM as adjunctive treatment in adult subjects with partial-onset seizures, and the experience with other AEDs in pediatric subjects, it is expected that LCM will also exhibit an acceptable benefit/risk profile in the pediatric population with uncontrolled generalized seizures.

In this study, the safety and tolerability of LCM will be studied when added to 1 to 3 concomitant AEDs in pediatric subjects with epilepsy syndromes associated with generalized seizures. The study will also obtain preliminary efficacy data of LCM on seizure frequency in pediatric epilepsy syndromes associated with generalized seizures.

This study is an exploratory study to investigate on which syndromes LCM has a beneficial effect in order to plan confirmatory study(ies) and exclude syndromes for which LCM has no clear benefit or possibly induces exacerbations.

Based on the currently available LCM pediatric safety and PK data from SP847 and SP1047, as well as on information available in the medical literature, the dosing recommendations for SP0966 are as follows:

- Lacosamide dosing should aim to achieve LCM plasma concentrations equivalent to the average steady-state LCM plasma concentration reached after a LCM 200 to 600mg/day dose administration in adult studies.
- A weight-based flexible dosing scheme is recommended:
 - Subjects <50kg: LCM 4-12mg/kg/day (oral solution)
 - Subjects ≥50kg: LCM 200 to 600mg/day (tablets/oral solution)

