7.2 Treatment(s) to be administered

Lacosamide will be administered orally bid (at approximately 12-hour intervals in the morning and in the evening). Administration of oral solution by feeding tube is permitted for subjects who are unable to swallow the oral solution. At the end of the Baseline Period and completion of Visit 2, subjects who meet the eligibility criteria will commence a 6-week Titration Period (LCM dosing flexibility allowed based on tolerability).

As described in Section 5.1, subjects will initiate treatment with LCM oral solution at 2mg/kg/day, or LCM tablets at 100mg/day based on body weight. The dose will be titrated to a level to optimize tolerability and seizure control, not to exceed 12mg/kg/day (oral solution) for subjects weighing <50kg, or 600mg/day (tablets/oral solution) in subjects weighing ≥50kg. Subjects will increase the LCM dose in a stepwise fashion on a weekly basis to optimize tolerability and seizure control (see Figure 5-1 and Figure 5-2). During the Titration Period only, back-titration is permitted.

The planned doses for each week of the Titration Period for subjects taking the LCM oral solution and tablet formulations are displayed in Table 7-1.

Table 7-1: Lacosamide dose titration during the Titration Period

Body weight category (formulation)	Flexible doses for the Titration Period by study week					
	Week 1	Week 2	Week 3	Week 4	Week 5	Week 6
<50kg (oral solution)	2mg/kg/day	4mg/kg/day	6mg/kg/day	8mg/kg/day	10mg/kg/day	12mg/kg/day
≥50kg (tablets/oral solution)	100mg/day	200mg/day	300mg/day	400mg/day	500mg/day	600mg/day

LCM=lacosamide

Note: Subjects weighing ≥50kg who are unable or unwilling to swallow tablets can be dispensed LCM oral solution instead.

After completion of Week 1, investigators will assess whether a subject would tolerate a further dose increase or whether a subject should hold the Week 1 dose for a longer duration. This hold will be at the investigator's discretion. The flexible LCM dosing over the remainder of the Titration Period is outlined in Table 7-2.

Table 7–2: Flexible LCM dosing during the Titration Period

Body weight category (formulation)	Target dose increase/week ^a (titration)	Dose decrease per back-titration step		Subsequent dose increase ^b (dose increase after back -titration step)	
		Min	Max	Min	Max
<50kg (oral solution)	2mg/kg/day	1mg/kg/day	2mg/kg/day	1mg/kg/day	2mg/kg/day
≥50kg (tablets/oral solution)	100mg/day	50mg/day	100mg/day	50mg/day	100mg/day

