- Dispense LCM. Subjects should take the first dose of LCM (based on body weight) in the clinic. The starting dose for subjects taking the oral solution formulation will be 2mg/kg/day, and the starting dose for subjects taking the tablet formulation will be 100mg/day.

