### **2.3 Study design and conduct**

SP0966 is a Phase 2, multicenter, open-label exploratory study designed to assess the safety and preliminary efficacy of oral LCM as adjunctive therapy for epilepsy syndromes associated with generalized seizures in pediatric subjects  $\geq 1$  month to  $< 18$  years of age.

The study treatment is LCM in either the oral solution formulation or tablet formulation. The formulation of LCM to be administered is based on the weight of the subject.

Subjects will not be randomized, but all subjects who sign the informed consent form at Visit 1 will be assigned a unique identification number.

Approximately 50 subjects will be enrolled at approximately 50 sites in Europe, and North America, and other regions as deemed necessary. It is planned to enroll approximately 40 subjects between 4 years and  $< 18$  years of age and at least 10 subjects between 1 month and  $< 4$  years of age.

The study will begin with subject screening at Visit 1 and will consist of a 6-week prospective Baseline Period. If all inclusion criteria are met and no exclusion criterion is met, the subject will begin a 6-week Titration Period (LCM dosing flexibility allowed based on tolerability) starting at Visit 2. Subjects will initiate treatment with LCM oral solution at 2mg/kg/day, or LCM tablets at 100mg/day based on body weight. The dose will be titrated to a level to optimize tolerability and seizure control, not to exceed 12mg/kg/day (oral solution) for subjects weighing  $< 50$ kg, or 600mg/day (tablets/oral solution) in subjects weighing  $\geq 50$ kg. Subjects will increase the LCM dose in a stepwise fashion on a weekly basis to optimize tolerability and seizure control.

At the end of the Titration Period (Visit 6), a 12-week Maintenance Period will begin. The LCM dose will remain stable throughout the Maintenance Period. Subjects who require a change in dose during the Maintenance Period will be withdrawn from the study.

The end of the Maintenance Period will be Visit 9, or, if subjects withdraw early, the ET Visit. Subjects may be eligible for participation in the additional open-label study (SP848). Subjects who choose not to participate in the open-label study or subjects who discontinue due to other reasons will enter a 2- to 4-week Taper Period followed by a Safety Follow-Up Visit 2 weeks ( $\pm 2$  days) after the final dose of LCM and a Safety Follow-Up Telephone Contact 30 days ( $\pm 1/+3$  days) after the final dose of LCM.

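### SAP 8.4 ties its only weight normalization of the mean daily dose to formulation, while the dosing unit depends on body weight, so children of 50 kg or more on oral solution have no stated conversion to mg/kg/day

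*SAP*

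**What the plan says.** SAP 8.4 (Extent of exposure) sets the unit of the summary: "The mean daily dose will be presented in mg/kg/day". It then gives its single conversion: "For patients who received tablets, the mean daily dose will be normalized by the baseline weight". The quantity being averaged is built from the dose records: "Total dose = (Morning dose + evening dose) x (administration stop date - administration start date + 1". That formula has no weight term, and no unit is given for the morning and evening doses.

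The protocol sets the dosing unit by weight category. Section 5.4 lists "Subjects <50kg: LCM 4-12mg/kg/day (oral solution") and "Subjects ≥50kg: LCM 200 to 600mg/day (tablets/oral solution"). Section 7.2 expressly allows the combination that matters here: "Subjects weighing ≥50kg who are unable or unwilling to swallow tablets can be dispensed LCM oral solution instead". The SAP's own design summary (section 2.3) agrees, capping the heavier group at 12 mg/kg/day's counterpart in mg/day for both formulations: "or 600mg/day (tablets/oral solution) in subjects weighing" 50 kg or more.

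**The concern.** The rule assumes that tablets mean mg/day and oral solution means mg/kg/day. The weight-based dosing scheme does not work that way: a child of 50 kg or more on oral solution is dosed in mg/day. No sentence in the SAP converts that child's dose.

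A programmer who applied the normalization only where it is prescribed could therefore average values in mg/day together with values in mg/kg/day. The mean, SD and maximum of the exposure summary would then be wrong. Because SAP 3.1 splits summaries by age group, the effect would be concentrated where the heavier children are, presumably the group aged 12 to under 18 years.

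**Working it through.** **1. Unit and rule side by side.**

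| Group | Dosing unit (Protocol 5.4 and 7.2; SAP 2.3) | Conversion in SAP 8.4 |
|---|---|---|
| Under 50 kg, oral solution | mg/kg/day | none stated; none needed if recorded per kg |
| 50 kg or more, tablets | mg/day | divide by Baseline weight |
| 50 kg or more, oral solution | mg/day | none stated |

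The third row is the gap.

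**2. Check on the plan's own figures.** The SAP gives no expected mean dose to reproduce. SAP 3.6 does state the dose range in both units, 2 to 12 mg/kg/day or 100 to 600 mg/day. Dividing by weight reconciles these at 50 kg: 100/50 = 2 and 600/50 = 12. Division by Baseline weight is therefore the right conversion, and the error from omitting it equals the weight in kg. For example, 400 mg/day is 400/50 = 8.0 mg/kg/day at 50 kg, 400/60 = 6.67 at 60 kg and 400/90 = 4.44 at 90 kg.

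**3. Dependence on the administration form.** Its unit is not given, so there are three cases.
- It follows the weight-based units: children of 50 kg or more on oral solution enter in mg/day, too high by a factor of 50 or more.
- It records mg for everyone: those children are unconverted, and so is every child under 50 kg, because the rule reaches only tablet takers.
- It records all oral solution in mg/kg: no error.

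**4. Illustrative size in the first case.** Assumptions, none from the documents: all other subjects at 8 mg/kg/day, and *k* affected subjects of 60 kg taking *x* mg/day. With *N* subjects, the mean is [(*N* − *k*) × 8 + *k* × *x*] / *N* unconverted; replace *x* by *x*/60 for the converted mean.

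| *N* | *k* | *x* (mg/day) | Mean, unconverted | Mean, converted |
|---|---|---|---|---|
| 50 | 1 | 200 | (392 + 200)/50 = 11.84 | 7.91 |
| 50 | 1 | 400 | (392 + 400)/50 = 15.84 | 7.97 |
| 50 | 1 | 600 | (392 + 600)/50 = 19.84 | 8.04 |
| 50 | 3 | 400 | (376 + 1200)/50 = 31.52 | 7.92 |
| 15 (assumed age group) | 1 | 400 | (112 + 400)/15 = 34.13 | 7.91 |

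For *N* = 50, *k* = 1 and *x* = 400, the SD is 55.4 and the maximum 400. The median stays at 8 in every row.

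**5. The same gap elsewhere.** SAP 10.1 groups plasma concentrations by dose level in mg/kg/day only (4-6, 7-8, 9-10, 11-12) and states no conversion. A dose held as 400 mg/day fits none of these bands until it is divided by weight.

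**The case against.** The strongest reply is that SAP 8.4 already commits to mg/kg/day for the whole summary without exception, so printing 400 for one child would breach the plan rather than follow it. This stands in part. A reader might infer that the SAP prescribes unconverted entry, but it does not say so. It states the target unit and leaves out how one group gets there.

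The second reply is that everything turns on an unseen form. This also stands. Some wording links the unit to formulation, for instance Protocol 8.2.1: "The starting dose for subjects taking the oral solution formulation will be 2mg/kg/day", with no weight limit given there, whereas Table 7-1 sets the starting dose by weight category. Those passages should be reconciled. They do not show how the form records dose, and only the third case in the working removes the problem.

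Third, a value of 200 or more in a mg/kg/day table is easy to spot: 400 is 33 times the stated limit of 12. The illustrative means are therefore not a forecast of what would be published.

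Three further inferences go beyond the documents:
- That this is the SAP's only dose-level summary. SAP 10.1 also works by dose level.
- That safety results depend on it. SAP 3.6 says summaries will in general not be split by dose, and no safety analysis uses the mean daily dose.
- That a formulation switch in Maintenance necessarily produces mixed units. A switcher who took tablets is arguably covered by the rule, and mixed units again presuppose the unseen form.

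**Conclusion.** The point holds as a minor but real defect. The conversion rule is keyed to formulation when the unit it must correct is keyed to body weight, and one expressly permitted group has no rule. The result is wrong if the administration form follows the weight-based units or records mg for everyone, and right only if all oral solution is recorded per kg.

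Where the error arises, each affected value is too high by a factor equal to the child's weight in kg. It distorts the mean, SD and maximum of the Maintenance Period mean daily dose, leaves the median little changed, and may carry over to the dose bands in SAP 10.1. No primary or secondary variable is affected. The number of affected children is not given, so the shift in the mean can only be illustrated, under the assumptions shown.

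**What to change.** In SAP 8.4, state the unit in which doses are recorded on the administration form, and replace the tablet sentence with:

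> Every dosing record in mg (or mg/day), whatever the formulation, will be divided by Baseline body weight before the mean daily dose is calculated; records already in mg/kg/day are used as recorded.

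Keying the rule to the recorded unit covers all three cases and any change of formulation.

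Apply the same rule when assigning dose levels in SAP 10.1. Converted doses need not be whole numbers (400/60 = 6.67 lies between two bands, and 200/60 = 3.33 lies below the lowest), so the band limits or a rounding rule should be stated there as well.

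The cost is a few words in two SAP sections and a line of programming. Baseline weight is already collected, and the protocol's data collection does not change.
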